#### 10.7.5.1 Reporting of Adverse Events

Events reported by the subject or observed by the (sub)investigator and that fall into any of the categories below must be recorded on the adverse event page of the CRF:

Table 2: Adverse Event Reporting for Visits until Week 20

Adverse Event	Inside treatment area	Outside treatment area including non-cutaneous events
BCC/SCC	All BCC/SCCs should be recorded in the CRF and reported to LEO as SAEs.	All serious and non-serious BCC/SCCs should be recorded in the CRF.  Serious BCC/SCCs should be reported to LEO as SAEs.
Other AEs	All AEs and SAEs should be recorded in the CRF.  Serious AEs should be reported to LEO as SAEs.	All AEs and SAEs should be recorded in the CRF.  Serious AEs should be reported to LEO as SAEs.

Table 3: Adverse Event Reporting for Visits after Week 20

Adverse Event	Inside treatment area	Outside treatment area including non-cutaneous events
BCC/SCC	All BCC/SCCs should be recorded in the CRF and reported to LEO as SAEs.	All serious and non-serious BCC/SCCs should be recorded in the CRF.  Only serious BCC/SCCs related to the treatment should be reported to LEO as SAEs.
Other AEs	All AEs and SAEs should be recorded in the CRF.  Serious AEs should be reported to LEO as SAEs.	Only SAEs related to the treatment should be recorded in the CRF.  These should be reported to LEO as SAEs.

*Please note: Local Skin Responses which match the criteria in the LSR Grading Scale are to be reported as LSRs in the CRF and not as AEs even if they require treatment. Any treatment should be recorded on the Concomitant medication page of the CRF together with the most important LSR (e.g. swelling should be reported as swelling-LSR).*

Adverse events should be described in the following manner:

The **nature** of the event will be described in precise English medical terminology (i.e. not necessarily the exact words used by the subject). Whenever possible, a specific diagnosis should be stated (e.g. allergic contact dermatitis).

For adverse events the anatomical **location** of the adverse event must be part of the adverse event description and may be described as the ‘in the selected treatment area’, ‘within 5 cm of the selected treatment area’, ‘more than 5 cm from the selected treatment area’ (with further specification for BCC/SCCs) or ‘not applicable’.

The **intensity** of the event will be described in terms of mild, moderate or severe according to the investigator’s clinical judgement.

- 
- **Mild:** The adverse event does not interfere in a significant manner with the subject's normal functioning level and requires no medical intervention.
  - **Moderate:** The adverse event interferes with the subject's normal functioning level and may or may not require medical intervention.
  - **Severe:** The adverse event produces significant impairment of the subject's functioning or requires medical intervention.

The **duration** of the event will be reported as the start date and stop date of the event.

For AEs recorded on Day(s) of starting treatment, it should be specified whether the AE started prior to or after first application of trial medication.

The **causal relation** of the event to the use of the investigational product will be described in terms of probable, possible, not related or not assessable according to the following:

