#### **10.7.5 Adverse Events**

*Any untoward medical occurrence in a patient or clinical investigation subject administered a pharmaceutical product and which does not necessarily have a causal relationship with this treatment. An adverse event (AE) can therefore be any unfavourable and unintended sign (including an abnormal laboratory finding), symptom, or disease temporally associated with the use of a medicinal (investigational) product, whether or not related to the medicinal (investigational) product. (ICH Harmonized Tripartite Guideline for Good Clinical Practice, E6 (R1)).*

---

A Serious Adverse Event (SAE) is any untoward medical occurrence that

- results in death
- is life-threatening
- requires inpatient hospitalisation or prolongation of existing hospitalisation
- results in persistent or significant disability/incapacity
- is a congenital anomaly/birth defect

or

- other medically important conditions\*), including SCC and BCC within the selected treatment area

\*) Events that may not be immediately life-threatening or result in death or hospitalisation but may jeopardise the subject or may require intervention to prevent one of the other outcomes listed in the definition above. Examples of such events are allergic bronchospasm, blood dyscrasias and convulsions.

Global Pharmacovigilance, LEO Pharma A/S is responsible for the assessment of headquarter expectedness according to LEO Pharma A/S procedures. The relevant reference document for this clinical trial is current version of the SmPC for ingenol mebutate gel (21) and subsequent updates as agreed between the head of Medical Department, and the medical director, Global Pharmacovigilance, LEO Pharma A/S. The current version of the SmPC for imiquimod (Aldara®) (appendix V) will be used for the assessment of expectedness for imiquimod.

At all visits, after Visit 1, the subject will be asked a non-leading question by the (sub)investigator: “How have you felt since I saw you last?” No specific symptoms will be asked for.

If there are no AEs to record (see [Table 2](#) and [Table 3](#) for reportable AEs), no further questions will be asked and “NO” should be stated. In case there are one or more AEs to record, “YES” should be stated and the investigator will record the event term, intensity, duration, suspected causal relationship to the investigational product and outcome.

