**Not assessable**

- The adverse event cannot yet be judged otherwise because present information is insufficient or contradictory. A final assessment (i.e. probably, possibly or not related) shall be made as more information becomes available, at the latest when the subject has completed the trial.

The **outcome** of the event will be classified and handled as follows:

- |                              |                                                                                                                                                                                                               |
|------------------------------|---------------------------------------------------------------------------------------------------------------------------------------------------------------------------------------------------------------|
| • Recovered/resolved         | The event has stopped. The stop date of the event must be recorded.                                                                                                                                           |
| • Recovering/resolving       | The subject is clearly recovering from an event. The event is, however, not yet completely resolved. Follow-up on the event is required until final outcome is established.                                   |
| • Not recovered/not resolved | Event is still ongoing. Follow-up on the event is required until final outcome is established.                                                                                                                |
| • Recovered with sequelae    | The event has reached a state where no further changes are expected and the residual symptoms are assumed to persist. An example is hemiparesis after stroke.
The stop date of the event must be recorded. |
| • Fatal                      | The subject has died as a consequence of the event. Date of death is recorded as stop date for the adverse event.                                                                                             |
| • Unknown                    | Unknown to investigator, e.g. subject lost to follow-up.                                                                                                                                                      |

---

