### **10.7.6 Serious adverse events**

#### **10.7.6.1 Reporting of Serious Adverse Events**

Any Serious Adverse Event (SAE), related or unrelated to the investigational product or any trial procedure after signature of the Informed Consent Form must be reported to LEO Pharma A/S on the (paper) **Serious Adverse Event Form – Clinical Trial** within **one calendar day, with the exception that:**

- After Week 20, non-related serious adverse events outside the treatment area should *not* be reported to LEO Pharma A/S (see [Table 2](#) and [Table 3](#))

---

An LSR classified as a SAE must be reported on the adverse event form in the CRF and reported to LEO Pharma A/S on the paper *Serious Adverse Event Form (SAE) – Clinical Trial*.

**Note:** Planned hospitalisation or planned prolonged hospitalisation do not fulfil the criteria for being an SAE. The elective nature of the event must be clearly documented in the subject's medical record.

SAEs must be reported on the adverse event form of the CRF book. Additionally reports must be made using the paper *Serious Adverse Event (SAE) Form – Clinical Trial*, supplied by LEO Pharma A/S. Apart from the assessment of the intensity, causal relationship to the investigational product(s) and/or trial procedures, the action taken and the outcome to date, this report must contain a comprehensive narrative description of the course of the event.

The completed LEO *Serious Adverse Event (SAE) Form – Clinical Trial* must be faxed or scanned and e-mailed Global Pharmacovigilance at LEO Pharma A/S:

LEO Pharma A/S Head Quarter  
Denmark, Global Pharmacovigilance  
[name]  
**Global Pharmacovigilance [contact]  
**E-mail:** [[contact]](mailto:[contact])

All other relevant reports of diagnostic procedures, hospital records, autopsy reports etc. must be included, as applicable or upon request from Global Pharmacovigilance.

The IRB(s)/IEC(s), regulatory authorities and concerned investigators will be notified of SAEs according to current regulation and local requirements.

All Suspected, Unexpected Serious Adverse Reactions (SUSARs) are subject to expedited reporting to regulatory authorities.

SAEs must be followed indefinitely until a final outcome has been established, i.e. the follow-up may continue beyond the end of the clinical trial.

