7.3.1 Censoring

Since the primary and secondary safety criteria are time-to-event analyses, a censoring scheme will be defined. This is not detailed in the CCTP.

Subjects from the safety analysis set will be included in the time-to-event analyses, as described in [Table 1](#):

Table 1: Censoring

Event	Date	Outcome
SCC	Date of biopsy	Event
Missing result from a biopsy	Date of biopsy	Censored
Trial completion without SCC	Date of last visit with assessment and no SCC	Censored
Trial discontinuation	Date of last visit with assessment and no SCC	Censored
Death from any cause	Date of death	Censored

SCC: Squamous cell carcinoma

In addition, a PP censoring will be defined, which is censoring at the time when a subject is excluded from the PP analysis set, as described in [Table 2](#):

Table 2: PP censoring

Event	Date	Outcome
Exclusion from PP analysis set with no documented SCC	Date of last visit with assessment before exclusion with no SCC	Censored

PP: Per protocol, SCC: Squamous cell carcinoma

Details on censored subjects are given by subject ID in the analysis set definition document.

Trial ID: LP0041-63	Date: 28-AUG-2019	Version: Final 1.0 Page 10 of 32
---------------------	--------------------------	-------------------------------------

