Appendix 2.7: Safety Data

Listing 7-1 Deaths

Listing 7-2 Serious adverse events

Listing 7-3 Subjects withdrawn from trial due to adverse events

Listing 7-4 Subjects withdrawn from trial due to LSRs

Listing 7-5 Severe adverse events

Listing 7-6 Adverse events

Listing 7-7 Suspicion of neoplasia and biopsy results

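### After Week 20 nothing assures that every death, with its date and cause, reaches the trial data, although the SAP censors at date of death from any cause and plans a listing of deaths

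*Protocol*

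**What the plan says.** **Recording and reporting of events.** Up to Week 20, Protocol Table 2 has all adverse events recorded. After Week 20, Table 3 narrows this. For other adverse events outside the treatment area, non-cutaneous events included, the rule is "Only SAEs related to the treatment should be recorded in the CRF". BCC and SCC outside the area are kept: "All serious and non-serious BCC/SCCs should be recorded in the CRF". Section 10.7.6.1 adds the matching limit on sponsor reporting: "After Week 20, non-related serious adverse events outside the treatment area should *not* be reported to LEO Pharma A/S". An event that "results in death" is serious by definition (10.7.5), but no sentence takes deaths out of the two limits.

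**Date of death in the protocol.** It is named once, in the outcome classification of 10.7.5.1 for a fatal event: "Date of death is recorded as stop date for the adverse event".

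**Other traces of a death.** Section 10.5 has reasons for withdrawal entered in the CRF, with an open category for reasons not listed. Section 10.7.7 includes the date of leaving the trial among CRF items to be verified against source. The SAP reports withdrawal reasons in Tables 1-3 and 1-4 and Listing 1-2.

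**Use of deaths in the SAP.** Table 1 of SAP 7.3.1 has a row "Death from any cause", censored at the date of death. Trial discontinuation is a separate row, censored at the last assessed visit free of SCC. SAP Appendix 2.7 plans "Listing 7-1 Deaths" with no restriction by period, location or relatedness. Neither place names a data source.

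**The concern.** The SAP needs an item that the protocol's event-recording rules do not reliably supply for most of follow-up. A subject who dies of an unrelated illness in year 2 or 3 has no event on the adverse event page and no report to the sponsor, and so has no fatal-event stop date.

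This is a safety trial run as a post-approval commitment (Protocol 8.2.1). It is open label (10.6.8) and has no trial committee (10.11). For a late fatal event of this kind, the investigator, who knows the treatment, decides whether it is related, and that decision settles whether the event and its cause enter the safety data. A call of unrelated also means that the sponsor receives no report to review. A deaths listing built on these data could look complete while mainly covering the first 20 weeks, and deaths by arm could not be read from it with confidence.

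**Working it through.** **1. The plan's own figure, used as a yardstick.** Protocol 10.3 gives 240 subjects per arm and upper 95% limits of 2.26% and 4.48% for 3-year rates of 1.0% and 2.5%. The formula is p + 1.96 × √(p(1 − p)/240):
- p = 0.010: 0.010 + 1.96 × 0.00642 = 2.26%, a half-width of 1.26 points.
- p = 0.025: 0.025 + 1.96 × 0.01008 = 4.48%, a half-width of 1.98 points.

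Both figures are reproduced.

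**2. One case followed through the documents.** Take a death at Month 24 from a non-cutaneous illness judged unrelated.
- Adverse event page: excluded by Table 3.
- Report to the sponsor: excluded by 10.7.6.1.
- Date of death: the only place named is the stop date of a recorded fatal event, and none is recorded.
- Withdrawal reason: possible under the open category, but death is not a named reason and no sentence requires it to be entered.
- Date of leaving: collected, but not defined as the date of death.
- Cause: not requested outside the event record.
- SAP Table 1: needs the date. If the date is absent, the discontinuation row is the natural fallback, though the SAP does not say so.

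**3. Length of the gap.** Week 20 is day 140, and the SAP uses 30.4375 days per month. 36 − 140/30.4375 = 36 − 4.6 = 31.4 months, and 31.4/36 = 87%.

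**4. Upper bound on deaths affected.** With 480 subjects and no dropout, 480 × 31.4/12 = 1,256 person-years. The documents give no mortality rate. At an assumed 1% to 4% per year:
- 1,256 × 0.01 = 13
- 1,256 × 0.04 = 50

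This counts every death after Week 20. It takes all of them as unrelated, outside the area and not due to BCC/SCC, with none captured through withdrawal data.

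**5. Effect on the primary estimate.** Kaplan-Meier estimates were simulated with 240 subjects per arm, exponential times to SCC and death, SCC found at the next scheduled visit, and 3,000 runs per scenario. Each death was censored first at its date and then at the last assessed visit. All deaths were treated as undated, including those before Week 20, which overstates the effect. The table gives the mean rise in the 3-year estimate, in percentage points.

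| 3-year SCC rate | Mortality 3% | Mortality 5% | Mortality 10% |
|---|---|---|---|
| 1.0% | 0.002 | 0.003 | 0.007 |
| 2.5% | 0.005 | 0.008 | 0.017 |

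Mortality here is over 3 years and is assumed. The largest change in any single run was 0.075 points. A rate of 4% per year is 1 − 0.96³ = 11.5% over 3 years. Scaling the largest mean in proportion gives 0.0165 × 11.5/10 = 0.019. All these values are small beside the half-widths of 1.26 and 1.98 points.

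**The case against.** The strongest reply is that Table 3 and 10.7.6.1 limit adverse-event recording and sponsor reporting, and do not limit recording that a subject died. A reader might infer that sites are told not to record deaths. The documents do not say that: the withdrawal reason and date of leaving are collected whatever the period or relatedness, and a death can be entered there. This part of the reply stands.

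The CRF is not among the documents, so a death page may exist. The SAP is dated August 2019, after the planned completion in Q2 2018. Its 7.5.6 drops one output because the item was not captured in the eCRF, and it says nothing similar about date of death. This is indirect evidence that the date was available. It is fair, but it does not show that collection was complete, and it says nothing about cause.

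Three further inferences go too far:
- That the primary analysis is compromised. The simulation shows a negligible shift.
- That 13 to 50 deaths will be missing. That range is a ceiling under the assumptions stated with it.
- That the plan promises all-cause mortality by arm. No objective or response criterion includes it, and the listing is titled only as deaths.

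What survives is narrower. The rules as written exclude these fatal events, the remaining route is optional and does not ask for the cause, and the SAP relies on a date with no stated source.

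**Conclusion.** The point holds as a gap in assured completeness. For about 31 of 36 months, capture of deaths other than those from BCC/SCC is assured only where the fatal event is inside the treatment area or judged related. The listing of deaths and the causes of death may therefore be incomplete, partly according to an unblinded judgement. At most about 13 to 50 deaths are affected, on an assumed annual mortality of 1% to 4%, no dropout and no capture through withdrawal data. The true number may be much smaller and cannot be found from the documents. The primary Kaplan-Meier estimate moves by under 0.02 percentage points on average at the protocol's assumed SCC rates, so the case for change rests on safety reporting.

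**What to change.** Add one exception to Protocol Table 3 and 10.7.6.1: every death up to Month 36 is recorded in the CRF with date and cause, whatever its location or relatedness. Leave the rest of the reduced rule unchanged. In the SAP, add a count of deaths by arm beside Listing 7-1.

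If data collection is over, amend the SAP only:
- name the source of the date of death;
- state that a death without a known date is censored at the last assessed visit;
- footnote Listing 7-1 with the restriction on event recording after Week 20.

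The cost is one protocol sentence, a date and a cause field if the CRF lacks them, and a few extra records per site. Even the upper bound of 50 deaths over 48 sites averages about one each.

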#### **Probably related**

- Follows a reasonable temporal sequence from administration of the investigational product
- Could not be reasonably explained by the subject's clinical state, environmental or toxic factors or other therapies administered to the subject
- Follows a known pattern of response to the investigational product
- Disappears or decreases on cessation or reduction in dose of the investigational product
- Reappears or worsens upon re-challenge

#### **Possibly related**

- Follows a reasonable temporal sequence from administration of the investigational product
- Could also be reasonably explained by the subject's clinical state, environmental or toxic factors or other therapies administered to the subject
- Follows a known pattern of response to the investigational product

#### **Not related**

- Does not follow a reasonable temporal sequence from administration of the investigational product

- 
- Is better explained by other factors like the subject's clinical state, environmental or toxic factors or other therapies administered to the subject
  - Does not follow a known pattern of response to the investigational product

**Not assessable**

- The adverse event cannot yet be judged otherwise because present information is insufficient or contradictory. A final assessment (i.e. probably, possibly or not related) shall be made as more information becomes available, at the latest when the subject has completed the trial.

The **outcome** of the event will be classified and handled as follows:

- |                              |                                                                                                                                                                                                               |
|------------------------------|---------------------------------------------------------------------------------------------------------------------------------------------------------------------------------------------------------------|
| • Recovered/resolved         | The event has stopped. The stop date of the event must be recorded.                                                                                                                                           |
| • Recovering/resolving       | The subject is clearly recovering from an event. The event is, however, not yet completely resolved. Follow-up on the event is required until final outcome is established.                                   |
| • Not recovered/not resolved | Event is still ongoing. Follow-up on the event is required until final outcome is established.                                                                                                                |
| • Recovered with sequelae    | The event has reached a state where no further changes are expected and the residual symptoms are assumed to persist. An example is hemiparesis after stroke.
The stop date of the event must be recorded. |
| • Fatal                      | The subject has died as a consequence of the event. Date of death is recorded as stop date for the adverse event.                                                                                             |
| • Unknown                    | Unknown to investigator, e.g. subject lost to follow-up.                                                                                                                                                      |

---

Upon completion of the last visit, an unscheduled visit may be required for any subject with an unresolved, treatment-related AE or LSR, if deemed clinically significant by the investigator.

Once a subject has completed the clinical trial, the investigator should follow up for outcome on all non-serious adverse events classified as possibly/probably related to the investigational product for 6 months or until final outcome is determined, whichever comes first.

